## 1 INTRODUCTION

This document describes the statistical analyses plan specified in the protocol D5170C00002. The scope of this plan addresses statistical analyses as they apply to safety and efficacy objectives, including the primary, intermediate and final analyses unless otherwise specified (e.g. analyses related to pharmacokinetic (PK) and translational science measurements will not be discussed in this document). A separate statistical programming plan (SPP), containing table templates and specifications, will be created to be used in conjunction with this document.

*The study, however, was early terminated; 29 subjects were randomized to one of the five treatment groups by the time of the study termination.*

## 2 STUDY OVERVIEW

*The following study objectives were copied from the original protocol. However, the study was early terminated; 29 subjects were randomized to one of five treatment groups by the time of the study termination. Due to the small number of subjects in the study, only descriptive statistics for limited efficacy endpoints are provided. However, all data will be listed.*

### 2.1 Study Objectives

#### 2.1.1 Primary Study Objective

To evaluate the efficacy of MEDI2070 versus placebo to induce clinical remission based on the CDAI score at Week 8 in subjects with moderate to severe Crohn's Disease (CD) who have failed or are intolerant to anti-TNF $\alpha$  therapy.

#### 2.1.2 Secondary Study Objectives

##### Induction Period Secondary Objectives:

1. To evaluate the efficacy of MEDI2070 versus placebo to induce remission at Week 16 based on the Simple Endoscopic Score for Crohn's Disease (SES-CD)
2. To evaluate the efficacy of MEDI2070 versus placebo to induce response at Week 16 based on the SES-CD
3. To evaluate the efficacy of MEDI2070 versus placebo to induce remission at Week 8 based on the Patient-reported Outcomes 2 score (PRO2)
4. To evaluate the efficacy of MEDI2070 versus placebo to induce response at Week 8 based on the PRO2
5. To evaluate the efficacy of MEDI2070 versus placebo to induce clinical response at Week 8 based on the CDAI

6. To evaluate the efficacy of MEDI2070 versus placebo to induce remission at Week 16 based on the PRO2
7. To evaluate the efficacy of MEDI2070 versus placebo to induce response at Week 16 based on the PRO2
8. To evaluate the efficacy of MEDI2070 versus placebo to induce clinical remission at Week 16 based on the CDAI
9. To evaluate the efficacy of MEDI2070 versus placebo to induce clinical response at Week 16 based on the CDAI
10. To demonstrate safety and tolerability of MEDI2070 therapy
11. To characterize the pharmacokinetics (PK) and immunogenicity of MEDI2070
12. To characterize the dose-response and exposure-response relationships

**Maintenance Period Secondary Objectives:**

1. To evaluate the efficacy of MEDI2070 versus placebo to induce clinical remission based on CDAI score at Week 28
2. To evaluate the efficacy of MEDI2070 versus placebo on remission at Week 28 based on the SES-CD
3. To evaluate the efficacy of MEDI2070 versus placebo on remission at Week 28 based on the PRO2
4. To evaluate the efficacy of MEDI2070 versus placebo on modified sustained remission, defined as remission at both Week 16 and at Week 28 based on the SES-CD
5. To evaluate the efficacy of MEDI2070 versus placebo on modified sustained remission, defined as remission at both Week 8 and at Week 28 based on the PRO2
6. To evaluate the efficacy of MEDI2070 versus placebo on modified sustained clinical remission, defined as clinical remission at both Week 8 and at Week 28 based on the CDAI
7. To evaluate the efficacy of MEDI2070 versus placebo on response at Week 28 based on the SES-CD

8. To evaluate the efficacy of MEDI2070 versus placebo on response at Week 28 based on the PRO2
9. To evaluate the efficacy of MEDI2070 versus placebo on clinical response at Week 28 based on the CDAI
10. To demonstrate safety and tolerability of MEDI2070 therapy
11. To characterize the PK and immunogenicity of MEDI2070

[REDACTED]

[REDACTED]

[REDACTED]

[figure not shown]
## 2.2 Study Design

This is a 3-part Phase 2b study comprising a 16-week, double-blind, placebo-controlled, induction period; a 12-week double-blind, placebo-controlled, maintenance period; and a 24-week, open-label period designed to evaluate the short-term efficacy and the short- and long- term safety of MEDI2070 in subjects with moderate to severe, active CD who have failed or are intolerant to anti-TNF $\alpha$  therapy as determined by the investigator. Subjects will be stratified based on the number of prior anti-TNF $\alpha$  agents that they have failed (1 versus > 1).

Approximately 342 subjects at approximately 300 centers worldwide will be randomly assigned to 1 of 5 treatment groups to receive intravenous (IV) and subcutaneous (SC) investigational product (MEDI2070 or placebo) once every 4 weeks (Q4W) during the double-blind, placebo-controlled induction and maintenance periods. Subjects who complete the double-blind, placebo controlled maintenance period (Week 28) will have the option to enter a 24-week, open-label period in which they will receive open-label MEDI2070 (210 mg SC) Q4W (Weeks 28 through 48). All subjects will be followed for safety at 3 visits over 28 weeks (Weeks 60, 70, and 80 for subjects completing the open-label period) after their last dose of investigational product.

***The study, however, was early terminated; 29 patients were randomized to one of the five treatment groups by the time of the termination.***

**Figure 2-1 Study Flow Diagram**

## 2.3 Treatment Assignment and Blinding

Subjects will receive investigational product (MEDI2070 or placebo) by IV infusion and/or SC injection at Week 0 (Day 1) then once Q4W during the 16-week, double-blind, placebo-controlled, induction period (i.e., Weeks 4, 8, and 12) and the 12-week double-blind, placebo-controlled, maintenance period (i.e., Weeks 16, 20, and 24). All subjects who complete the double-blind maintenance period will have the option to enter the 24-week open-label treatment period. All subjects entering the open-label period will receive open-label MEDI2070 (210 mg SC) once Q4W (i.e., Weeks 28, 32, 36, 40, 44, and 48).

A total of approximately 342 subjects will be randomly assigned to one of five treatment groups:

Treatment Group	Double-blind Treatment Period				Open-label Period
	Induction			Maintenance	
	Week 0	Week 4	Weeks 8, and 12	Weeks 16, 20, and 24	Weeks 28, 32, 36, 40, 44, and 48
Treatment Group 1 High (n = 76)	700 mg MEDI2070 IV + placebo SC	700 mg MEDI2070 IV + placebo SC	210 mg MEDI2070 SC	210 mg MEDI2070 SC	210 mg MEDI2070 SC
Treatment Group 2 High-medium (n = 76)	280 mg MEDI2070 IV + placebo SC	210 mg MEDI2070 SC + placebo IV	210 mg MEDI2070 SC	210 mg MEDI2070 SC	210 mg MEDI2070 SC
Treatment Group 3 Low-medium (n = 76)	210 mg MEDI2070 SC + placebo IV	105 mg MEDI2070 SC + placebo IV	105 mg MEDI2070 SC	105 mg MEDI2070 SC	210 mg MEDI2070 SC
Treatment Group 4 Low (n = 38)	70 mg MEDI2070 SC + placebo IV	35 mg MEDI2070 SC + placebo IV	35 mg MEDI2070 SC	35 mg MEDI2070 SC	210 mg MEDI2070 SC
Treatment Group 5 Placebo (n = 76)	Placebo SC and IV	Placebo SC and IV	Placebo SC	Placebo SC	210 mg MEDI2070 SC

IV = intravenous; SC = subcutaneous

*The study, however, was early terminated; 29 subjects were randomized to one of the five treatment groups by the time of the study termination.*

## 2.4 Sample Size

With a total sample size of approximately 342 and a randomization ratio of 2:1:2:2:2, the sample sizes are 76, 38, 76, 76, and 76 for placebo and MEDI2070 low, low-medium, high-medium, and high dose groups, respectively. A 10% dropout rate is assumed for each treatment group during the induction period.

Assuming a placebo CDAI remission rate of 12% and MEDI2070 high dose CDAI remission rate of 31% at Week 8 of the induction period, approximately 76 subjects per treatment group will provide at least 85% power to detect a 19% difference in CDAI remission rates at Week 8 between MEDI2070 high dose versus placebo, using a two-sided test at a significance level of  $\alpha = 0.10$ . The minimum detectable difference in CDAI remission rates at Week 8 will be 11%.

Assuming a 5% placebo SES-CD remission rate and 20% MEDI2070 high dose SES-CD remission rate at Week 16 of the induction period, the given sample size will provide at least 81% power to detect a 15% difference in SES-CD remission rates at Week 16 between MEDI2070 high dose versus placebo using a two-sided test at a significance level of  $\alpha = 0.10$ . The minimum detectable difference in SES-CD remission rates at Week 16 will be 10%.

*The study, however, was early terminated; 29 subjects were randomized to one of the five treatment groups by the time of the study termination.*

## 3 Statistical Methods

### 3.1 General Considerations

All data will be provided in data listings. Tabular summaries for limited efficacy and safety parameters in the double-blind treatment period will be presented by treatment group.

All efficacy data will be summarized using the analysis visits. The analysis visit windowing rules will be defined based on study days of post-baseline. The details of analysis visit windowing rules will be described in Section 3.4.

Day 1 will be defined as the day of first investigational product administration. For any variable, unless otherwise defined, the baseline value is the last non-missing assessment taken prior to the first

investigation product administration. The change from baseline will be calculated by subtracting the baseline values from the individual post-baseline values. If either the baseline or post-baseline value is missing, the change from baseline is set to missing.

The following conventions will be applied to all data presentations and summary.

- For continuous endpoints, arithmetic mean, and median will be formatted to one more decimal place than the measured value. SD will be formatted to two more decimal place than the measured value. Minimum and maximum values will be presented with the same number of decimal places as the measured value.
- For categorical variables, the count and percentage of responses will be presented in the form XX (XX.X%) where the percentage is in the parentheses.
- Data analyses will be conducted using SAS® version 9.4 (SAS Institute Inc., Cary, NC) or higher.

### 3.2 Analysis Populations

The analysis populations are defined in Table 3-1.

**Table 3-1 Analysis Populations**

Population	Description
Intent-to-treat (ITT) population	The Intent-to-Treat (ITT) Population includes all subjects who are randomized into the study and receive at least one whole dose of investigational product for the 28-week, double-blind, placebo-controlled treatment period. Subjects will be analysed according to their randomized treatment group, regardless of whether they receive an investigational product that is different from what they were randomized to.
Safety population	The Safety Population includes all subjects who receive at least one dose of investigational product. Subjects will be analyzed according to the actual treatment received during the placebo-controlled, double-blind treatment period even if it is different from what the subject is randomized to.
Open-label population	Open-label population includes all subjects who are enrolled in the open-label treatment period and have at least one dose of open-label MEDI2070 210 mg SC treatment.
PK population	The Pharmacokinetics (PK) Population includes all subjects who receive at least one dose of investigational product and have at least one PK sample containing detectable MEDI2070.

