### **4.8.3 Analysis Populations**

Details of each population below and any additional population, if needed, will be described in the SAP.

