#### **4.8.3.1 Intent to Treat Population**

The ITT population includes all subjects who are randomized into the study and receive any dose of investigational product for the 28-week, placebo-controlled, double-blind period. Subjects will be analyzed according to their randomized treatment group, regardless of whether subjects receive an investigational product different from that they were randomized to. The ITT population will be used as the primary population for all efficacy analyses. Disposition summary, demographics, baseline characteristics, protocol deviation, and efficacy endpoints will utilize this analysis population.

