#### **4.8.3.2 As-treated Population**

The as-treated population includes all subjects who receive any amount of investigational product. Subjects will be analyzed according to the actual treatment received during the placebo-controlled, double-blind period even if it is different from that the subject was randomized to. Analysis of safety endpoints and summary of investigational product administration from the placebo-controlled, double-blind period will utilize this analysis population.

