**Table 3.2-1 Analysis Populations**

Population	Description
Intent-to-treat (ITT) population	The Intent-to-Treat (ITT) Population includes all subjects who are randomized into the study and receive at least one dose of investigational product for the 28-week, double-blind, placebo-controlled treatment period. Subjects will be analysed according to their randomized treatment group, regardless of whether they receive an investigational product that is different from what they were randomized to.
As-treated population	The As-treated Population includes all subjects who receive at least one dose of investigational product. Subjects will be analyzed according to the actual treatment received during the placebo-controlled, double-blind treatment period even if it is different from what the subject is randomized to.
Open-label population	Open-label population includes all subjects who are enrolled in the open-label treatment period and have at least one dose of open-label MEDI2070 210 mg SC treatment.
PK population	The Pharmacokinetics (PK) Population includes all subjects who receive at least one dose of investigational product and have at least one PK sample containing detectable MEDI2070.

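### The final SAP limits ITT to subjects with at least one whole dose, an undefined condition that the protocol does not contain

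*Combined protocol and SAP*

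**What the plan says.** Two SAPs are bound with the protocol. The final SAP is the one that records the early termination with 29 subjects randomised; the earlier SAP does not mention termination. The entry conditions read:

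| Population | Source | Condition |
|---|---|---|
| ITT | Protocol 4.8.3.1 | "includes all subjects who are randomized into the study and receive any dose of investigational product" |
| ITT | Earlier SAP, Table 3.2-1 | "randomized into the study and receive at least one dose of investigational product" |
| ITT | Final SAP, Table 3-1 | "randomized into the study and receive at least one whole dose of investigational product" |
| Safety | Final SAP, Table 3-1 | "The Safety Population includes all subjects who receive at least one dose of investigational product" |
| Open-label | Final SAP, Table 3-1 | "have at least one dose of open-label MEDI2070 210 mg SC treatment" |

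The PK row of Table 3-1 also asks for one dose, without *whole*. For its as-treated set the protocol says: "The as-treated population includes all subjects who receive any amount of investigational product" (section 4.8.3.2). Protocol 4.8.3 defers to the SAP: "Details of each population below and any additional population, if needed, will be described in the SAP".

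In the final SAP, ITT is the set for the primary summary (3.6.1.2), the secondary summaries (3.6.2.2) and the baseline tables (3.5.2).

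**The concern.** The word *whole* appears in one row of one table, and that row defines the primary analysis set. It adds an entry condition that depends on what happened during dosing, after randomisation. No reason is visible.

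The word also cannot be applied as it stands. At Weeks 0 and 4 every arm has two components; the high-medium arm at Week 0, for example, receives "280 mg MEDI2070 IV + placebo SC" (final SAP 2.3). The text does not say whether *whole* means both components in full, the active one, or either. Two programmers could set different ITT flags from the same records.

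At stake is the denominator of the remission rates. A randomised, partly dosed subject could be in the Safety population but not in ITT. Such a subject never reaches the non-responder rule of section 3.3.3.

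**Working it through.** The plan gives no count of subjects affected, so there is no figure of its own to reproduce. The check has two parts: reading the definitions together, and an illustration of scale.

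**1. Who is removed.** Table 3-1 asks for one whole dose at any time in the 28-week double-blind period, not a whole first dose. The treatment table in final SAP 2.3 shows dosing at Weeks 0, 4, 8, 12, 16, 20 and 24, which is seven visits. The last five are subcutaneous only. A subject is therefore excluded only if none of the seven doses was whole. The two-component ambiguity matters only for someone with no whole dose from Week 8 onward.

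**2. What such a subject's Week 8 outcome would be.**
- Protocol 4.1.6 stops investigational product when a scheduled double-blind dose is not received within its window. It then provides 28 weeks of safety follow-up.
- The Note to File (final SAP, Appendix 6.3) adds that follow-up CDAI could not be entered after an early termination visit until a workaround was issued late in 2017.
- In practice, then, the excluded subject is mainly someone who stopped early after incomplete dosing and usually has no Week 8 CDAI. Under section 3.3.3 that subject, if kept in ITT, is a non-responder.

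**3. Effect on one arm.** With r remitters among n subjects, removing one non-responder changes the rate from r/n to r/(n − 1), a rise of r/[n(n − 1)]. This is zero when r = 0 and positive otherwise.

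**4. Scale.** Inputs from final SAP 2.4 are 29 randomised and a 2:1:2:2:2 ratio.
- Expected size of a full-size arm: 29 × 2/9 = 6.4.
- Expected size of the low arm: 29 × 1/9 = 3.2.

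Actual arm sizes and remission counts are not given. An assumed split is high 6, placebo 6, the two medium arms 7 each and low 3 (6 + 6 + 7 + 7 + 3 = 29). Removing one subject with a missing outcome gives:

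| Arm size | Remitters | Before | After | Change (points) |
|---|---|---|---|---|
| 6 | 0 | 0/6 = 0% | 0/5 = 0% | 0 |
| 6 | 1 | 1/6 = 16.7% | 1/5 = 20.0% | +3.3 |
| 6 | 2 | 2/6 = 33.3% | 2/5 = 40.0% | +6.7 |
| 6 | 3 | 3/6 = 50.0% | 3/5 = 60.0% | +10.0 |
| 7 | 2 | 2/7 = 28.6% | 2/6 = 33.3% | +4.8 |
| 3 (low) | 1 | 1/3 = 33.3% | 1/2 = 50.0% | +16.7 |

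**5. Effect on a difference.** Assume high 2/6 and placebo 1/6, a difference of 33.3 − 16.7 = 16.7 points (from unrounded rates).
- One removal from high gives 2/5 − 1/6 = 23.3 points.
- One removal from placebo gives 2/6 − 1/5 = 13.3 points.

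The sign of the shift depends on which arm loses the subject. If no subject lacked a whole dose, every change is zero.

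**The case against.** The best defence is that the protocol leaves population details to the SAP, and that its two phrases, any dose for ITT and any amount for the as-treated set, leave room for the SAP to settle what a dose is. The definition may also exist out of sight: the dose-preparation text in protocol 4.5.1 is largely redacted, and the separate programming plan is not in these documents. The earlier SAP planned to summarise subjects who received the entire dose (3.5.3), which suggests that dose completeness could be determined.

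Part of this stands. The protocol's wording is slightly loose, and *whole* may be defined somewhere not visible. But supplying details does not explain a stricter entry condition, and a definition elsewhere would not remove the conflict with the protocol's any dose. Final SAP 3.2 presents Table 3-1 as the place where populations are defined, so the meaning belongs there. The final SAP's own exposure section (3.5.3) has dropped the entire-dose summary, so no exposure table it names would show how many subjects the word removes.

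The defence is also right about reach. Site staff give every dose (protocol 4.5.5), and one whole dose at any of seven visits is enough to stay in ITT.

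**Conclusion.** The concern holds as a minor defect of wording. The final SAP's ITT row departs from the protocol without a visible reason or definition, and the subjects it removes would mostly have counted as non-responders. Under the assumed counts, one removal raises an arm's rate by 0 to 10.0 points in an arm of six and by 16.7 points in a low arm of three with one remitter. The true effect may be nil. All of this rests on assumed arm sizes, remission counts and at least one subject with no whole dose.

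Four stronger readings are tempting, and the documents do not support them:
- *Any incomplete first dose removes a subject.* It does not, because a later whole dose restores eligibility.
- *The word favours active treatment.* Only the high and high-medium arms receive active intravenous product at Week 0, and protocol 5.3.2 describes infusion reactions as common at first exposure, so a link to treatment is conceivable. Nothing shows that it occurred, and the direction between arms is unknown.
- *Removing an observed remitter could swing the comparison widely.* That subject would need a Week 8 score despite never having had a whole dose. This is possible but implausible, and should not be used to show scale.
- *A true intention-to-treat set has been lost.* The protocol's set already required some dosing, so this is a change of degree.

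The consequences are limited further. Efficacy is descriptive only (final SAP 2 and 3.6.1.2), so no test or error rate is touched. Disposition uses everyone randomised (3.5.1), and all data are listed.

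**What to change.** In the ITT row of Table 3-1, replace the whole-dose condition with the protocol's any dose, and add as the SAP's own clarification that a partial dose counts. Nothing else needs to change: analysis by randomised group is already in the same row, and non-responder imputation is already in section 3.3.3. If the sponsor has a reason to keep *whole*, the SAP should give it, define the term for visits with two components, and report by arm how many dosed subjects it removes.

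The cost is a few words in one table and, if it is already programmed, an update of the ITT flag. No new data are needed.

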### 3.3 Handling of Dropouts and Missing Data

Subjects may be missing specific data points for a variety of causes. In general, data may be missing due to a subject’s early withdrawal from study, a missed visit, or inability to evaluate an endpoint at a particular point in time. The general procedures outlined below describe what will be done when a data point is missing. Missing safety endpoints will not be imputed.

#### 3.3.1 Missing and Incomplete Dates

For any listings, missing or incomplete dates will be listed as is.

In the case where the start or stop date of an event or medication is missing or incomplete, the following rules will be applied in the analysis:

**Table 3-2 Missing Dates Imputation Rules**

	Missing	Imputation	Exception
Start date (Adverse Events and concomitant medication)	Day	01	Default to Study Day 1 if an event starts the same year and month as Study Day 1 and Stop date is after Study Day 1
	Day/Month	01JAN	Default to Study Day 1 if an event started the same year as Day 1 and Stop date is after Study Day 1
	Day/Month/Year	No imputation	
Stop date (concomitant medication)	Day	Last day of the month	Default to the End of Study Date or the primary analysis cut-off date for ongoing subjects if the concomitant medication stopped the same year and month as the End of Study Date or primary analysis cut-off date
	Day/Month	31DEC	Default to the End of Study Date or the primary analysis cut-off date for ongoing subjects if the concomitant medication stopped the same year as the End of Study Date or primary analysis cut-off date
	Day/Month/Year	No imputation	

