### 3.5.4 Prior and Concomitant Medications

*Prior medication* refers to all medications that were started prior to the start of the first dose of investigational product.

*Concomitant medication* refers to all medications taken during the treatment period of the DB period and the OL period. Concomitant medications include medications continued from pre-treatment.

Medications with missing start and stop dates will be counted as concomitant medications.

Medications with partial start or stop dates will be handled as described in Section 3.3.1. Medications with start and stop dates which bracket the first dose date will be flagged as both prior and concomitant medications.

All prior and concomitant medications data will be coded by World Health Organization Drug Dictionary, version March 2017 or newer and listed for each subject by treatment groups.

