#### **3.8.1.2 Treatment-Emergent AEs during DB Treatment Period**

For subjects entering the OL treatment period, the TEAE will be defined as any AE with onset on or after the administration of the first dose of blinded investigational product up to the day prior to administration of the first OL SC dose. For subjects not entering the OL treatment period, the TEAE will be defined as any AE with onset on or after the administration of the first dose of blinded investigational product up to and including 28 weeks post last blinded dose.

All TEAEs including TESAEs, Adverse Event of Special Interest (AESIs), and TEAEs leading to permanent discontinuation of investigational product will be summarized overall. The TEAEs with severity grades will be summarized by grades assigned by National Cancer Institute Common Terminology Criteria for AEs (NCI CTCAE) V4.0. Tabular summaries of the TEAEs during the DB treatment period will be provided as follows:

- Incidence rate of TEAEs by SOC and PT
- Incidence rate of TEAEs by SOC, PT, and severity
- Incidence rate of related TEAE by SOC and PT
- Incidence rate of TESIs by SOC and PT

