### **3.8.1.3 TEAEs during OL Treatment Period**

TEAE for the OL treatment period will be defined as any AE with onset on or after the administration of the first open-label SC dose of MEDI2070 up to and including 28 weeks post-last dose. Incidence rate of TEAEs during OL treatment period will be summarized by SOC and PT using the OL population.

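### Final SAP Table 3-2 has no start-date rule at the first open-label dose, so some partially dated adverse events that began on open-label MEDI2070 are tabulated under the blinded arm, placebo included

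*Combined protocol and SAP*

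**What the plan says.** Table 3-2 of the final SAP imputes start dates for adverse events (AEs) and concomitant medications.

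- **Day missing:** set to the 1st. The exception is "Default to Study Day 1 if an event starts the same year and month as Study Day 1", and it also requires a stop date after Study Day 1.
- **Day and month missing:** set to 1 January. The exception is "Default to Study Day 1 if an event started the same year as Day 1 and Stop date is after Study Day 1".
- **Wholly missing:** "No imputation".

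The stop-date rows cover concomitant medication only, so an AE stop date is used as recorded.

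Section 3.1 fixes the anchor: "Day 1 will be defined as the day of first investigational product administration". Section 3.4.2 defines a separate OL Period Study Day 1, which Table 3-2 never mentions.

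TEAEs are divided at that second date. For subjects who enter the open-label period, section 3.8.1.2 runs the double-blind window "up to the day prior to administration of the first OL SC dose". Section 3.8.1.3 then counts "any AE with onset on or after the administration of the first open-label SC dose of MEDI2070". Under section 2.3, all open-label entrants receive the same MEDI2070 regimen, whatever their randomized arm.

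For undated medications section 3.5.4 has a rule: "Medications with missing start and stop dates will be counted as concomitant medications". AEs have no counterpart. Section 3.8.1 lists every AE and counts a specific event once per subject.

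**The concern.** The table applies a sensible principle at one boundary and omits it at the other. At first dose, an event that could have begun on treatment is moved up to the dose date, provided it ended later. At the first open-label dose, the default of the 1st of the month or 1 January pulls the event back across the boundary. A complete stop date after the open-label dose does not prevent this.

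At stake is attribution. A former placebo subject's event on active drug can be printed in the placebo column and be absent from the open-label table. Section 3.8 keeps only TEAEs and laboratory evaluations as summarized double-blind safety results, and section 3.8.1.3 keeps an open-label TEAE table. The affected tables are therefore among the few that remain.

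A wholly undated AE raises a related question: both TEAE windows are defined by onset date, and the SAP does not say where such an event goes.

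**Working it through.** The plan states no figure on this point, so there is none to reproduce. The check applies Table 3-2 literally and then the two TEAE windows.

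**Inputs.** Section 3.6.2.1 places Week 24 at Day 169 (7 × 24 + 1), so Week 28 is Day 197, which is 196 days after first dose. The 24-week open-label period is 168 days. The full open-label TEAE window, to 28 weeks after the Week 48 dose, is 20 × 7 + 28 × 7 + 1 = 337 days. Assumptions: first open-label dose on Day 197, uniform onset, first doses spread over a four-year calendar, and resolved events stopping 10 days after onset.

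**Worked cases.**

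| First dose | First open-label dose | True onset | Missing | Imputed start | Table |
|---|---|---|---|---|---|
| 5 Sep 2016 | 20 Mar 2017 | 23 Mar 2017 | day | 1 Mar 2017 | double-blind |
| 5 Sep 2016 | 20 Mar 2017 | 23 Mar 2017 | day, month | 1 Jan 2017 | double-blind |
| 5 Feb 2016 | 19 Aug 2016 | 22 Aug 2016 | day, month | 5 Feb 2016 | double-blind |

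In each case the stop date (2 Apr 2017 or 1 Sep 2016) is complete and falls after the open-label dose.

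**Direction.** For an onset after first dose, the imputed date (the 1st, 1 January or Study Day 1) is never later than the true onset. The rule can move an open-label onset back, but it cannot move a double-blind onset forward.

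**Day missing.** Only the calendar month of the first open-label dose is exposed.
- With a mean month of 365.25/12 = 30.4 days, the open-label days left in that month average (30.4 + 1)/2 = 15.7.
- A dose on the 1st causes no error, which removes (1/30.4) × 30.4 = 1.0 day and leaves 14.7.
- Share moved: 14.7/15.7 = 93.6% of open-label onsets in that month; 14.7/168 = 8.8% over 24 weeks; 14.7/337 = 4.4% over the full window. Enumerating every date gives the same figures.

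**Day and month missing, stop date present.** Onsets in the calendar year of the first open-label dose move, unless that dose was on 1 January. For a window of L days the share is 1 − (L − 1)/(2 × 365.25) − 1/365.25.
- L = 168: 1 − 0.2286 − 0.0027 = 76.9%.
- L = 337: 1 − 0.4600 − 0.0027 = 53.7%.

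**Day and month missing, no stop date, 24 weeks.** Enumeration gives 53.7% double-blind, 23.2% pre-treatment and 23.1% open-label. The pre-treatment share arises because the exception needs a stop date. When both first doses fall in one year, 1 January precedes the first blinded dose.

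**Fully dated events:** 0% misassigned.

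**Scale.** 29 randomized × 2/9 = 6.4 expected on placebo. One subject is 1/7 = 14 to 1/6 = 17 percentage points, at most.

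**The case against.** The strongest counter-reading is that Study Day 1 is period-specific, since sections 3.4.1 and 3.4.2 define one for each period. A day-missing event in the crossover month with a later stop date would then be set to the first open-label dose and counted once, correctly. The text is not free of ambiguity. But section 3.1 defines the unqualified Day 1 as first dose of investigational product, and Table 3-2 uses Day 1 and Study Day 1 interchangeably without either period prefix. The first-dose reading is the natural one, and if the other was intended the table should say so.

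The second objection is materiality, and most of it stands. The study stopped at 29 subjects, section 3.8 makes no statistical safety comparisons, and the documents do not say how many subjects entered the open-label period or how many AEs have partial dates. Because a specific event counts once per subject, a misassigned event changes an incidence only if that subject had no such double-blind event already. The 14 to 17 points are therefore an upper bound for one subject, not a typical effect.

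A reader might also infer that the rule shrinks the MEDI2070-placebo safety contrast. The documents do not support this. All five arms cross to the same open-label drug, so the blinded MEDI2070 arms can gain misdated open-label events as well.

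**Conclusion.** The gap is real and narrow. Applied as written, Table 3-2 gives a wrong period for most partially dated AEs that began on open-label drug in the crossover month (day missing) or crossover year (day and month missing), and usually charges them to the randomized blinded arm. The shares rest on the uniform-onset and Day 197 assumptions; the mechanism does not. The number of affected AEs is unknown and may be zero, and the effect on between-arm differences is not determinable.

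Three stronger readings should be resisted.

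- **Open-label events in general are misassigned.** Fully dated events, and day-missing events in later months, are placed correctly.
- **Partial dates always go to the blinded arm.** Some year-only events without a stop date become pre-treatment, and some remain open-label.
- **Wholly undated AEs drop out of every TEAE table.** This is a plausible inference, but the SAP does not state it. Their classification is unspecified, they remain in the AE listing, and section 1 leaves table specifications to a separate programming plan that is not among the documents.

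**What to change.** Amend Table 3-2 for AEs.

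1. **Open-label exception.** This applies to subjects who entered the open-label period. If the partial start date matches the month and year of OL Period Study Day 1 (or the year, when the month is also missing) and the stop date is not before that day, set the start to OL Period Study Day 1. State that this takes precedence over the Study Day 1 exception, because both match when a year-only date falls in a year containing both first doses.
2. **Wholly missing start date.** Treat the AE as treatment-emergent unless its stop date precedes first dose. For an open-label entrant whose stop date is missing, or is on or after the first open-label dose, show the event as period-unassigned. A blanket default to Study Day 1 would send undated open-label events to the blinded arm, which is the error being corrected.
3. **Footnote** the number of AEs placed by each rule. If none is affected, the footnote shows it.

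The cost is a few lines of SAP text, a small program change and one extra table line. The downside is that some true double-blind onsets with partial dates move to the open-label table. With the day missing these come from the days just before the first open-label dose; with a year-only date they may come from earlier in that year.
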